## 1. STUDY SUMMARY SCHEMA

#### Literature review

**Objective:** To establish and review the known data

#### Training of pathologists in Digital Pathology

All pathologists participating in the study who do not use DP as part of regular practice will be trained on DP. Training sets will be created for each site (covering all the specialties) where training is required. Up to 30 samples (minimum 20 plus practise slides) reviews will be required for each untrained pathologist in DP. Sample mix will include a range of samples including biopsies and resection, simple, complex and variety of stains (H&E, special and immunocytochemistry). Training will be ratified per RCPath guidelines.

#### Pilot study and survey of pathology staff

**Pilot study: Sample size:** 20 (renal) and 40 (breast, GI and skin) including difficult samples. **Duration:** 10 weeks. **Objective:** To test the working practices of the study for any unforeseen problems. **Design:** Based on the methodology of the main study.

#### Focus groups/key informant interviews

**Objective:** To identify potential barriers and facilitators to the adoption of DP. **Design:** Focus groups and key informant interviews. **Sample:** Convenience sample of pathology and laboratory staff in each study site. **Analysis:** Thematic analysis of qualitative data.

#### Main study

Sample size: 2000 slide sets from 5 sites (Coventry, Belfast, Lincoln, Oxford, Nottingham). Primary Objective: To compare pathologists' diagnoses made by assessment of glass slide microscopy (LM) of breast, GI, skin and renal samples, with the same pathologists' diagnoses of the same samples (intra-rater reliability) using digital whole slide imaging (DP). Study design: A multi-centre, randomised cohort study comparing interpretation of slides by pathologists using LM and DP. Enrolment: Samples will be enrolled between July 2019 and April 2021 from five participating NHS histopathology departments. Data analysis: Concordance will be quantified in this study as complete agreement, clinically unimportant difference.

Sec	ondary objectives			
Eye tracking	Qualitative study	Health Economics		
Objective: To measure how pathologists examine DP images to establish if the technique of examining these images contributes to error in interpretation	Objective: To explore views and experiences of pathologists and laboratory staff migrating from LM to DP.	Objective: To assess the incremental costs involved in DP vs LM-based pathology		
Design: Visual search parameters including overall search time, visual search patterns, the initial Areas of Interest (AOI) in the sample and visual fixation times will be observed.	Occurrence: At initiation of main study and 12 months into the study	Design: Data from existing deployments of DP in the study group will inform the estimates of cost to		
Analysis: Visual search behaviour will be statistically linked to initial DP expertise and also to the development of DP expertise by the less DP experienced participants through the study.	Design: Qualitative study utilising face-to-face/telephone semi- structured interviews Data analysis: Thematic analysis	implement DP. A micro- costing exercise will then be carried out to assess the impact of DP on process efficiency.		

Page **8** of **38** 

## 2. INTRODUCTION

Digital pathology (DP) refers to the use of high throughput slide scanners to digitise diagnostic histopathology slides that are then reported on computer workstations as opposed to a conventional microscope. Such a development allows pathologists to report samples remote from the laboratory producing slides. In addition to providing some mitigation to the mismatch of pathologist capacity to workload present in many NHS hospitals, there are important implications for sharing difficult samples more easily, which may help reduce error, and for low volume high complexity specialties such as renal pathology, that also require pathologist expertise out of hours. Prior to widespread adoption, it is important to demonstrate that current DP solutions are fit for the purpose of providing the pathologist with tissue imaging of sufficient quality to ensure diagnostic accuracy equivalent to the brightfield and immunofluorescent light microscopy (LM) which is the current standard of care. A number of comparison studies have already been published but the majority have not been adequately powered to provide data of non-inferiority. Concerns have been expressed by researchers as to whether there is sufficient evidence of equivalence to enable full-scale deployment of DP in the NHS, particularly in respect of the breast and colorectal cancer screening programmes.

Moreover, since the image produced in most DP systems is inferior to resolution provided by LM, it is questionable as to whether sufficient numbers of challenging samples have been examined in the data published, to prove equivalence, particularly in specialties requiring fine resolution such as renal biopsy interpretation. In addition, none of the published studies have examined the use of DP in immunofluorescence, which is essential if the DP is going to be used for renal biopsies.

This study is designed around teams of four pathologists, blind to the original diagnoses, all examining the same series of samples, using both LM and DP. The modality each pathologist views/reports on first will be randomised for each batch of samples, and there will be a minimum of a six-week washout period between LM and DP viewings. Reports will then be scrutinised by a trained Research Fellow independent of the reporting pathologists. Differences detected will be classified by an independent pathologist into clinically important (would alter the clinical management) or clinically unimportant (would not alter the clinical management). The original diagnosis will serve as the reference diagnosis. The ground truth (GT) for each sample is decided on conclusion of the readings, by consensus of the study pathologists, taking into account the reference diagnosis. This allows comparison of each pathologist's performance on LM and DP against the GT. The study will examine 2000 histopathology samples including 600 samples each of breast, gastrointestinal (including 200 cancer screening samples) and skin, and 200 renal samples taken for native or transplant related renal disease. The renal biopsies will include immunofluorescence for detection of immunoglobulin deposits. The population of samples enrolled will be a combination of sequentially selected samples and those from study centres' archives. With the exception of renal, samples will also be enriched with at least 10% moderately difficult and at least 10% difficult samples.

A Health Economic evaluation will involve estimating the core costs and benefits associated with DP, compared with LM. This will involve estimating the impact of switching to DP on throughput, and translating this into the impact on the time to establishing a treatment plan. It will further involve assessing samples of discrepancy to investigate the impact on treatment decisions, and the incremental costs and benefits resulting from this impact. This will be for all discrepancies if feasible, or a purposive sample (selected based on material impact on health and cost outcomes).

A qualitative study will examine, by means of focus group and semi-structured interview, the barriers and facilitators to DP and perceptions and experiences of pathologists and laboratory staff prior to, and during, the progress of the study. Eye tracking hardware will examine pathologists' examination techniques and this will be analysed alongside reporting discrepancies to identify if poor technique contributes to errors in reporting.

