While most previous studies show good LM/DP agreement, (6) (7, 8) (9) some (10) raise concerns over the suitability of DP for diagnosis. Particular concern has been raised about the use of DP for examining samples taken as part of the NHS cancer screening programmes for breast, bowel and cervical cancers.

Our team includes UK leaders in pathology at six NHS teaching hospitals and a large pathology network. We have world leading experience in DP having pioneered its use in routine practice, as well as vast experience of pathology practice and research. The pathologists taking part are a diverse group including highly experienced, relatively junior, early adopters of DP and - a majority - new to DP. The study plan is based on eight viewings of each sample by four pathologists with LM and also with DP, culminating in a consensus ground truth (GT), enabling measurement of agreement within and between readers. Samples enrolled will reflect routine practice. The samples will include cancer screening biopsies and will be enriched for areas of difficulty such as dysplasia (7, 10, 11). State-of-the-art DP equipment designed for diagnosis and holding either CE or FDA approval will be used in this study.

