## 4. STUDY DESIGN

This is a multi-centre validation comparison study comparing pathologists' diagnoses using digital whole slide imaging (DP) with their diagnoses using glass slide light microscopy (LM), the current standard practice within the NHS. The order in which the pathologists view the images (DP and LM) will be randomised.

To achieve objectivity, we have introduced a washout period of a minimum of six weeks between the two viewings (LM and DP) of the same sample by the same pathologist.

An integrated pilot study will test the working practices and processes of the study for any unforeseen problems. It also aims to assess whether it is feasible to include at least 10% difficult cases and 10% moderate cases for the skin, GI and breast specialties. The results of this study will be reviewed by the Study Steering Committee.

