## 7. SAMPLE PATHWAY

## 7.1 Sample selection criteria

Histopathology samples from five participating NHS trusts will be selected. All samples are collected for the purpose of routine histopathology reporting and only entered into the study on completion of their clinical review at the respective NHS participating site.

There are four sub-specialty areas that are included in the study: breast, gastrointestinal (GI), skin and renal. The sample selection process will be devised to include cancer screening biopsies and will be enriched (20%) for areas of difficulty, with the exception of renal samples where all are considered difficult cases:

- Breast (Belfast, Coventry, Lincoln & Nottingham): A total of 600 samples including at least 200 cancer screening biopsies enriched with:
  - o At least 10% resected tumours (moderately difficult)
  - 10% difficult samples: low grade ductal carcinoma in situ, atypical hyperplasia, screening category B3 and B4, lesions with calcium oxalate (Weddellite calcification), sclerosing and papillary lesions, and micrometastases
- GI (Coventry, Belfast & Nottingham): A total of 600 samples including at least 200 cancer screening biopsies enriched with:
  - At least 10% resected tumours (moderately difficult)
  - 10% difficult: oesophageal dysplasia, polyp cancers, inflammatory bowel disease, minimal change colitis, graft versus host disease, giardiasis, cytomegalovirus, H. pylori and herpes virus infection
- Skin (Coventry, Belfast & Lincoln): A total of 600 samples enriched with:
  - o At least 10% non-basal cell carcinoma cancer resections (moderately difficult)
  - 10% difficult: sentinel nodes, dysplastic naevi, spitz naevi, lentigo maligna, early and desmoplastic melanoma, herpes virus infection, leischmaniasis, leprosy, amyloid, angioscaroma, and Kaposis sarcoma
- Renal (Oxford only): A total of 200 sequential native biopsies for glomerular, tubulointerstitial and vascular disease and transplant biopsies for graft rejection. No enrichment is planned in the renal biopsy group as all of these biopsies are difficult to report.

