#### Figure 3: Sample reporting

**Legend:** Belfast, Coventry, Lincoln and Nottingham enrol reported samples of breast, gastrointestinal and skin. Renal biopsy samples are enrolled by Oxford only. These samples are divided into batches and randomised to which pathologists review on DP first and which on LM first (Read 1). Curved arrows indicate circulation of batched samples between the LM reviewing pathologists. After 6 weeks, pathologists swap to the alternative platform in Read 2. For each sample where there is considered to be a clinically important difference between reports, participating pathologists meet after read 2 to agree the ground truth diagnosis.

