## **12.2** Statistical analysis plan

#### Primary analysis

There will be three categories for the level of agreement: complete agreement, clinically unimportant difference and clinically important difference. For each sample, three sets of agreements will be reported:

- whether each pathologist's DP and LM diagnoses concur
- whether each of the four DP diagnoses concur with the GT
- whether each of the four LM diagnoses concur with the GT

Two measures will be used to quantify concordance: percentage concordance and ICC. Logistic regression models will be used to estimate the probability that diagnoses are concordant and will include a random effects term to account for multiple results per sample.

For cancer resections, as well as diagnosis, comparisons will also be made across all RCPath dataset items.

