In addition to these publications, UHCW, the lead trust and sponsor, plans a series of press releases and media interviews on the progress and findings of the studies. We plan reports to the NHS Patient Safety Group regarding the costs of pathology errors, the role of DP in reducing error through improved expert and peer review of samples, and findings of the eye tracking study.

Generalisability of findings across pathologists with different levels of expertise:

The study pathologists are all NHS consultants and range in experience from 3 to 35 years consultant experience, working in a mix of teaching hospital and district general hospital pathology departments across the UK. The study will recruit a trainee pathologist as its Research Fellow. Three pathologists are already using digital pathology for routine practice.

We will develop a strategy in consultation with our PPI group and UHCW/Warwick University Communications team (e.g. a lay summary of the findings available on the study websites, and dissemination through social media) to help patients, patient representatives and wider public learn about the project's findings.

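### The ground truth takes in the routine, probably mostly LM, diagnosis and no platform masking is stated for the consensus, so the secondary DP-versus-GT and LM-versus-GT comparisons may lean to LM

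*Protocol*

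**What the plan says.** **How GT is set.** Section 2 states: "The original diagnosis will serve as the reference diagnosis". GT is then decided, once the readings are finished, "by consensus of the study pathologists, taking into account the reference diagnosis". The Figure 3 legend (Section 7.7) says that, for samples with a clinically important difference between reports, "participating pathologists meet after read 2 to agree the ground truth diagnosis".

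**How GT is used.** Section 12.2 asks, for each sample, "whether each of the four DP diagnoses concur with the GT", and asks the same of the four LM diagnoses. Section 6 lists agreement with GT under secondary outcomes. The primary outcome there is each pathologist's own DP-LM agreement.

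**Where the reference diagnosis comes from.** Under Section 7.1 samples are "only entered into the study on completion of their clinical review at the respective NHS participating site". The modality of that clinical review is not stated. Section 4 describes the comparator as "glass slide light microscopy (LM), the current standard practice within the NHS". On the other side, Section 19.2 notes: "Three pathologists are already using digital pathology for routine practice". Section 3 describes the readers as including "early adopters of DP and - a majority - new to DP".

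**Masking.** Section 7.5 keeps readers unaware of the reference diagnosis when they read. Section 18.5 has a non-reporting pathologist decide which reports are discordant, without knowing author or platform. Neither section covers the meeting that agrees GT.

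**The concern.** A standard used to compare two modalities should not draw more on one of them than on the other. Here GT can draw on four DP reads, four LM reads and one further opinion, which is probably LM in most cases. If pathologists tend to make the same mistake on glass, an LM reference diagnosis will sometimes share it. It then pulls GT towards the LM reads, and correct DP reads are counted as errors. A panel that knows which report came from which platform could produce a similar pull.

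This is incorporation bias. At stake are the DP-versus-GT and LM-versus-GT agreement rates, and the cost-of-error work so far as it uses GT. These results would be read as showing which modality is closer to the truth, so even a modest tilt matters. The rule also has to be right before the meetings take place. Once a panel has seen the reference diagnosis, a consensus formed without it cannot be recovered.

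**Working it through.** **1. The plan's own figure.** The protocol gives no precision for agreement with GT. The nearest figure is the margin in Section 12.1: design effect 1 + 0.8 × (4 − 1) = 3.4; 2400 / 3.4 = 705.9; 1.96 × √(0.9 × 0.1 / 705.9) = 2.21%. This reproduces the stated 2.2%. It applies to DP-LM pair concordance within one specialty, not to a difference between DP-GT and LM-GT agreement, so it is not a yardstick here.

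**2. Counting the inputs.** Each reader contributes one LM and one DP read, so the readers' part is balanced at 4 v 4. Where one reader's two reads differ, the other inputs are three LM reads, three DP reads and the reference diagnosis. If the reference is LM, that is at most 4 v 3.

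**3. Direction and size by simulation.** All inputs below are assumptions.

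- 400,000 samples, four readers, two modalities, equal true accuracy on LM and DP.
- Each read has a latent score √0.3·S + √v·M + √0.1·R + √(0.6 − v)·e. S is the sample, M the modality effect shared by all reads of that sample on that modality, R the reader and e residual noise. The read is wrong if the score falls below the normal quantile of (1 − accuracy).
- Shared modality variance v = 0, 0.1 or 0.2. True accuracy is 90% or 75%. (The 90% in Section 12.1 is expected DP-LM concordance, a different quantity.)
- The reference diagnosis shares S and the M of its own modality. It is LM in 100%, 75% or 50% of samples.
- GT is the majority of the eight reads plus the reference, which counts as 0, 1 or 4 reads. Ties are split at random. Simulation noise is about 0.1 point.

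LM minus DP agreement with GT, in percentage points:

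| True accuracy | v | Reference left out | All LM, weight 1 | All LM, weight 4 | 75% LM, weight 1 | 75% LM, weight 4 | 50% LM, weight 4 |
|---|---|---|---|---|---|---|---|
| 90% | 0 | −0.04 | 0.02 | −0.03 | 0.03 | −0.01 | 0.02 |
| 90% | 0.1 | 0.06 | 0.16 | 0.59 | 0.06 | 0.26 | 0.01 |
| 90% | 0.2 | 0.01 | 0.38 | 1.45 | 0.14 | 0.73 | 0.00 |
| 75% | 0 | 0.10 | 0.05 | −0.01 | 0.01 | 0.03 | −0.01 |
| 75% | 0.1 | 0.06 | 0.38 | 1.80 | 0.19 | 0.83 | 0.01 |
| 75% | 0.2 | −0.07 | 1.20 | 3.76 | 0.55 | 1.83 | 0.03 |

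**4. Reading the table.** With the reference left out, the lean is zero within noise, but both modalities are flattered: at 75% true accuracy each shows about 80% to 81%. With no shared modality error, or with a reference that is half LM, there is no lean. A lean needs both a mostly LM reference and shared error. No scenario favours DP beyond noise.

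**5. Limits.** A vote stands in for a discussion, GT is applied to every sample, and the effect of an unmasked meeting is not modelled.

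**The case against.** The strongest reply has five parts.

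- **The primary outcome is clean.** Intra-pathologist DP-LM agreement does not use GT, and an independent pathologist blind to platform classifies the discrepancies. This stands in full. A reader might infer from Section 12.2, which lists the GT comparisons under its primary analysis, that the main result is tilted. Section 6 does not support that.
- **Readers setting their own standard need not favour LM.** This also stands. It inflates both modalities about equally. The lean can come only from the reference diagnosis or from an unmasked meeting.
- **The reference may not be mostly LM.** The protocol never states its modality, Section 3 says the team pioneered routine DP, and some readers use DP routinely. The inference remains reasonable, because LM is described as standard practice and most readers are new to DP, but it is an inference.
- **Silence is not proof.** Masking of the meeting may be set out in a document not shown. That is fair, but taking in the reference diagnosis is fixed in the protocol and does not depend on masking.
- **The reference is the only input from outside the study reads.** Dropping it leaves GT resting wholly on the readers being scored. This is a real trade-off and a reason to report both versions.

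A reader might also infer that the tilt could never be checked later. The enrolment lists in Sections 7.2.1 and 7.2.3 are open-ended and samples remain traceable to their site, so the documents show only that modality is not specified as an item.

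**Conclusion.** The point holds for the secondary comparisons with GT, and for the cost-of-error work so far as it uses GT. The rule builds the routine diagnosis into the standard. If that diagnosis is mostly LM and errors are partly shared within a modality, the comparison may lean to LM.

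The size cannot be found from the documents. Under the assumptions above it is about 0 to 1.5 points at 90% accuracy, and 0.2 to 0.4 point there when an all-LM reference counts as a single read and errors are shared. Values near 4 points need 75% accuracy, an all-LM reference worth four reads and the larger shared error.

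A reader might reach larger figures by a shortcut. Take the 10% of pairs expected to differ, assume truth lies equally often with each modality, and let GT follow LM in a share p of them. The apparent advantage is 0.10 × (2p − 1), which is 1.0, 2.0 or 4.0 points at p = 0.55, 0.60 or 0.70. Nothing in the protocol supports any of these values of p, and setting the results against the 2.2% margin compares different quantities. The shortcut is not evidence of size.

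Section 2 (GT for each sample) and the Figure 3 legend (a meeting only where there is a clinically important difference) also need reconciling. If the legend governs, the meeting's influence is confined to those samples.

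**What to change.** Amend the GT rule in Section 2 and the Figure 3 legend to two recorded steps:

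1. The panel sees the reports with reader and platform removed and records a provisional consensus before the reference diagnosis is disclosed.
2. The reference diagnosis is disclosed and the final GT is recorded.

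Report the DP-GT and LM-GT comparisons against both. Read a DP-LM difference that appears only with the final GT as possible incorporation bias.

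Add an enrolment field for the modality of the reference diagnosis (LM, DP or both) and repeat the comparison by that field. State how GT is set for samples that do not go to a meeting.

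The cost is one extra entry per consensus case, one database field, some preparation of masked reports and slightly longer meetings. The final GT is kept, so no information is lost. Masking will be imperfect, since readers may recognise their own reports.

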## 3. BACKGROUND & RATIONALE

The use of digital whole slide imaging to view histopathology slides offers a number of potential benefits to pathology departments. It allows the pathologist to view the slides remote from their site of production, thereby allowing work to be moved easily between pathologists, either to assist flow, provide multi-disciplinary, expert or out of hours review, or review where patients move between sites for treatment. Digitising the slides also allows the use of computer algorithms to help improve pathologists' performance. The potential benefits offered by digital pathology (DP) will only be fully delivered once it becomes the preferred method of examining microscope slides. Reluctance amongst pathologists to use DP is partly based on a lack of comprehensive multi-centric evidence proving that DP is safe to use for primary diagnosis. Reluctance to change may also be due to the fear of adopting unfamiliar technology. For disruptive innovations to spread beyond early adopters to the majority of users, clear evidence of relevance is required (1). The impact of DP on productivity and efficiency has not been studied so the return on investment is unknown preventing business sample development. We plan a large multi-centric light microscopy (LM)/DP comparison study with multiple pathologist viewings to address this need.

Histopathological diagnosis using LM is the key step in many major disease pathways. Advances, particularly around early detection of cancer and improved life expectancy, are placing additional burdens on overstretched Cellular Pathology resources (2). This is partly because early stage disease is more difficult to detect leading to more challenging and often increased numbers of samples, and partly because greater data are required from these samples to provide the best standard of care. There is an emerging crisis of Cellular Pathology NHS consultants: 32% of consultants are over 55 and expected to retire within 5 years; the number of new consultants is less than half the number expected to retire; and 55% of the histopathology departments surveyed hold vacancies (2). DP offers better productivity, efficient workload distribution and centralised slide production. This delivers economies of scale and improved access of tissue blocks for molecular analysis which is important for personalised medicine (3, 4). Improved diagnostic accuracy by peer and expert review of samples (5) is greatly increased by DP.

While most previous studies show good LM/DP agreement, (6) (7, 8) (9) some (10) raise concerns over the suitability of DP for diagnosis. Particular concern has been raised about the use of DP for examining samples taken as part of the NHS cancer screening programmes for breast, bowel and cervical cancers.

Our team includes UK leaders in pathology at six NHS teaching hospitals and a large pathology network. We have world leading experience in DP having pioneered its use in routine practice, as well as vast experience of pathology practice and research. The pathologists taking part are a diverse group including highly experienced, relatively junior, early adopters of DP and - a majority - new to DP. The study plan is based on eight viewings of each sample by four pathologists with LM and also with DP, culminating in a consensus ground truth (GT), enabling measurement of agreement within and between readers. Samples enrolled will reflect routine practice. The samples will include cancer screening biopsies and will be enriched for areas of difficulty such as dysplasia (7, 10, 11). State-of-the-art DP equipment designed for diagnosis and holding either CE or FDA approval will be used in this study.

